### 18.10 EGD Data Collection

## Esophagogastroduodenoscopy (EGD) data collection

Date and Time EGD performed \_\_\_\_\_ Initials person filling out form \_\_\_\_\_

Where was EGD performed? Inpatient outpatient

Provider reading EGD \_\_\_\_\_

Rank of person performing EGD

Attending GI

Attending General Surgery

GI Fellow 1st Year

GI Fellow 2nd Year

GI Fellow 3rd Year +

### IN THE ACCOMPANYING EGD (ENDOSCOPY), IS THERE EVIDENCE OF THE FOLLOWING?

#### (Circle all that apply)

- a. Clean stomach and duodenum, i.e., no fresh blood or coffee ground
- b. Upper GI pathology non-causative/ incidental.
- c. A LOW grade non-Variceal lesion (Forrest IIc, III)
- d. A HIGH Grade Non-Variceal Lesion (Forrest Ia, Ib, IIa or IIb)
- e. Coffee ground blood
- f. Fresh blood or evidence of active bleeding.
- g. Varices (either gastric or esophageal) or Variceal Hemorrhage
- h. Other sources of bleeding

Other sources of bleeding

-Mallory-Weiss

-Angiodysplasia

-Gastritis

-Esophagitis

-Tumor

#### i. If there is a bleeding source detected, where is it?

Esophagus

Stomach

Duodenum

None detected

#### j. Did you perform endoscopic hemostasis?

Yes

No

If yes, what intervention? \_\_\_\_\_

### 18.11 Patient Satisfaction Day 7 and Day 30

## Patient Satisfaction Day 7 and Day 30

I understood the reason for the pill camera

Strongly Agree

Agree

Neutral

Disagree

Strongly Disagree

I understood the procedure for the pill camera.

Strongly Agree

Agree

Neutral

Disagree

Strongly Disagree

I felt the research team answered all my questions Yes No

The pill camera was easy to swallow Yes No

I would use the pill camera again Yes No

Did you have any issues Yes No

if Yes, what are they? \_\_\_\_\_

### 18.12 Patient Follow-up Telephone Call Day 7 and Day 30

## Patient Follow up Telephone Call Day 7 and Day 30

Initials of person completing form \_\_\_\_\_

You came to the ER on {date of visit} for possible bleeding.

Are you experienced the same or similar symptoms? Yes No

Please tell me what they are \_\_\_\_\_

(If patient is continuing to have symptoms please list)

Have you recently noticed blood in the stool? Yes No

Have you vomited any BRIGHT RED or COFFEE GROUND blood recently? Yes No

How long how has this episode of BLEEDING lasted?

Between 1-2 days

Between 3-4 days

Between 5-7 days

Never went away

Unsure

**Have you noticed any bloody or black tar stools in the past 24 hours? Yes No**

**Have you passed out or lost consciousness in the past 24 hours? Yes No**

**Have you seen a gastroenterologist since you were discharged? Yes No**

**Did you have an upper endoscopy while you were in the hospital? Yes No**

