Patients will be advised not to have an MRI for 30 days and to consult with their doctor prior to receiving an MRI in the future. For patients who are unsure whether they excreted the PillCam, *an abdominal X-Ray may be required as an outpatient to confirm passage.*

In order to maximize safety for all study subjects, only consented and enrolled subjects will be administered the PillCam under the personal supervision of the PI or under the supervision of a sub-investigator/trained research associate responsible to the PI. In addition, the PillCam will be stored in a secure, limited access area. Product accountability log must include the protocol number, investigative site name, product name, medical units (i.e., video capsules), serial number and subject ID number.

We anticipate low cognitive risk to participants. Diagnosis of source of gastrointestinal bleeding lesion is presumably one of the reasons the patient presented for emergency care. We do not anticipate an affective risk to participants. Some participants may be bothered by the knowledge that the device will pass naturally and may take several days to be excreted.

We believe the study poses a low privacy risk to subjects as all data will be encrypted and no PHI will be stored with data.

Finally, the study has a low economic risk since the device and the interpretation of the device are not being billed to the subject or his/her insurance company. *The only economic risk may result from an unanticipated complication of the device that will not be covered by Medtronic, LTD, the manufacturer of the pill camera, GWUH or MFA.*

Minor adverse events that occur will be reported directly to the principal investigator and overall study coordinator at the next business day. Minor adverse events include inability to tolerate capsule, discomfort swallowing capsule, issues regarding video capture, issues regarding video transmission, erroneous video interpretation that has no significant impact on clinical care, protocol deviations, reactions to medication (pro-motility agent), delays in endoscopy interpretation, delays in EGD and others. All minor adverse events will be shared with the entire research team at regularly scheduled monthly calls or sooner at the PI's discretion.

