## 7.6 Adverse Event Reporting

Detailed information concerning adverse events will be collected and evaluated throughout the conduct of the protocol. Results of clinical observations, laboratory tests, and reported events form the basis for evaluating the safety profile of this therapy. At all contacts, patients will be questioned regarding side effects or symptoms associated with the study medication which are as follows:

- Difficulty swallowing the PillCam UGI
- Capsule stuck in the stomach or bowel
- Inability to pass PillCam naturally through a bowel movement
- Surgical intervention
- Aspiration
- Possible skin irritation from the sensors

The clinical center will report adverse events to the coordinating center in a timely fashion. The coordinating center will summarize and report adverse events to the DSMB.

Additional procedures are warranted for cases of serious adverse events which is defined by the FDA as a patient outcome that is: (1) death; (2) life-threatening, i.e., the patient was at substantial risk of dying at the time of the adverse event or it is suspected that the use or continued use of the product would result in the patient's death; (3) hospitalization (initial or prolonged); (4) disability, i.e., resulted in a significant, persistent, or permanent change, impairment, damage or disruption in the patient's body function/structure, physical activities or quality of life; (5) congenital anomaly, i.e., there are suspicions that exposure to a medical product prior to conception or during pregnancy resulted in an adverse outcome in the child; (6) requires intervention to prevent permanent impairment or damage. Serious adverse events will be reported immediately to the Study PI, site PI and the local IRB. The PI will notify the DSMB.

The only indication for breaking the randomization code is when it is medically necessary to unmask the study drug assignment to be able to treat the patient, such as an allergic reaction or severe side effect that appears to be related to the medication.

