**Did you have an upper endoscopy after being discharged from the hospital? Yes No**

**What were the results of the endoscopy?**

Bleeding resolved

Bleeding persisted

New problem

Unsure

If patient has a new problem, please describe. \_\_\_\_\_

Did you have a return visit to the hospital? Yes No

Return date to the hospital? \_\_\_\_\_

Which Hospital? \_\_\_\_\_

Where you hospitalized for recurrent bleeding? \_\_\_\_\_

Did you have a second endoscopy? Yes No

What were the results? \_\_\_\_\_

When were you discharged? \_\_\_\_\_

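### The Day 7 and Day 30 form limits black stools and syncope to the past 24 hours and leaves the other bleeding items without a start point, so resolved episodes without hospital contact may be under-recorded

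*Combined protocol and SAP*

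**What the plan says.** Section 3.2 lists re-bleeding and capsule-specific events among the serious adverse events to be reported at Day 7 and Day 30, under Other Outcomes. Section 4.4 (step 14) gives detection of adverse events and recurrent bleeding as the purpose of the two contacts, by telephone for subjects at home and in person for those still in hospital.

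The form in Section 18.12 contains:

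- black stools: "Have you noticed any bloody or black tar stools in the past 24 hours";
- syncope: "Have you passed out or lost consciousness in the past 24 hours";
- blood in stool: "Have you recently noticed blood in the stool";
- vomited blood: "Have you vomited any BRIGHT RED or COFFEE GROUND blood recently";
- general symptoms: "Are you experienced the same or similar symptoms", with a free-text line;
- items with no recall limit on seeing a gastroenterologist or having an endoscopy after discharge, on hospitalization for recurrent bleeding and on a second endoscopy, and "Did you have a return visit to the hospital", with the date of return.

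On the capsule, Section 7.6 says that patients will be questioned at every contact about a list that includes "Inability to pass PillCam naturally through a bowel movement". Section 2.3.1 makes a possible outpatient X-ray depend on the answer: "For patients who are unsure whether they excreted the PillCam". The form in Section 18.12 has no item on capsule passage.

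**The concern.** Melena is one of the presenting signs that qualify a patient for the trial (Section 5.1), so its return is a natural marker of re-bleeding. A 24-hour window suits the ED intake form (Section 18.5), where the same wording appears. It does not suit contacts that look back over 7 days and then 23 days. A subject who had black stools on Day 3, or fainted on Day 15, and had recovered by the next call can truthfully answer no to the item that names the event.

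The trial's stated goal is to test whether patients can be discharged safely. Section 11.3 compares adverse events between arms with a chi-square test. Under-recording in both arms leaves fewer events, makes a difference harder to detect, and lowers the absolute rate that would be offered as evidence of safety.

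**Working it through.** The plan states no figure for follow-up capture, so there is none to reproduce. The check counts the days that the recall windows reach, then asks what the other items add.

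**Inputs.** Contacts on Days 7 and 30 (Section 7.5). Participation of 30 days (Protocol Summary). A 24-hour window on the black-stool and syncope items (Section 18.12). For the control arm, an assumed hospital stay of 4 days, taken from the background median of 4.0 days in Section 2.1, with a range of 2 to 6 days.

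**Calendar coverage of the two 24-hour items.**

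- Up to Day 7: 1/7 = 14.3%.
- Days 8 to 30: 1/23 = 4.3%.
- Overall: (1 + 1)/30 = 6.7%, leaving 28/30 = 93.3% outside the window.

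**If symptoms last more than a day.** Assume that onset is equally likely on each of the 30 days and that symptoms last k days. An item then registers an episode that is still present on Day 7 or Day 30, which is 2k of the 30 onset days:

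- k = 1: 2/30 = 6.7%
- k = 2: 4/30 = 13.3%
- k = 3: 6/30 = 20.0%

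These figures are for the two items alone. They are not capture rates for re-bleeding.

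**What the other items add.**

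- The two items that say recently may reach back further, but each patient and interviewer sets the limit. The form asks about black stool separately from blood in the stool, and a patient with tarry stool may not call it blood.
- The general symptom item has no stated window, and its prompt concerns symptoms that are continuing, so a resolved episode can be answered no.
- The bleeding-duration item gives a length, not an onset date.
- The items on gastroenterologist visits, endoscopy and return to hospital have no recall limit. They reach any bleed that led to one of those contacts.
- Checking against the electronic record is done only where necessary (Section 8.7). Chart review (Section 18.13) records transfusion, further endoscopy, hemostatic therapy and surgery.

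The gap that remains is an episode that resolved between calls without such care.

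**Difference between arms.** Days at home outside the 24-hour windows = 30 − days in hospital − 2.

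- Discharged from the ED: 30 − 0 − 2 = 28.
- Admitted for 4 days: 30 − 4 − 2 = 24.
- Admitted for 2 to 6 days: 26 to 22.

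The arms differ by 2 to 6 days, all early in follow-up. The shared gap of 22 days or more is much the larger part.

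**The case against.** A reader might infer that re-bleeding is missed on most follow-up days, mainly in people sent home, and that the safety comparison therefore favours CERA. The documents do not support this, for four reasons.

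- The two 24-hour items are not the whole of capture. The same form prompts for similar symptoms, for recent blood in stool or vomit, and for every kind of later care, most of it without a time limit. A figure of 2 in 30 describes two questions, not the yield of the call.
- The listed outcome is serious adverse events. Under the definition in Sections 7.6 and 10.2, most serious re-bleeds would involve hospitalization or intervention, which the untimed items and the chart review are built to find. A brief, untreated melena at home is the likeliest loss, and it is not clearly part of that outcome.
- Both arms receive the same contacts on the same days, and controls are also at home for most of the 30 days. Discharged CERA subjects are to be scheduled for an outpatient EGD within 3 days (Section 4.4), which is an early clinical check.
- Section 7.6 already requires staff to ask about capsule passage, the satisfaction form (Section 18.11) has an open question on issues, and the adverse event form rates relationship to the PillCam. The lack of a field does not show that the question goes unasked.

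All four stand, and they limit the point. They do not remove it. The documents give no definition of re-bleeding that would exclude milder episodes, and Section 4.4 says that the calls are meant to find recurrent bleeding. The printed window on the one item that names black stool still does not match the interval it serves. An answer on capsule passage still has no place on the follow-up form.

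**Conclusion.** The point holds as a defect in the form's wording. The black-stool and syncope items cover 2 of 30 days, and the other bleeding-symptom items have no defined window or onset date. Resolved melena or syncope without hospital contact may therefore be under-recorded in both arms, possibly somewhat more in subjects discharged early.

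Neither the amount nor any bias between arms can be sized. The documents give no timing of re-bleeds, no share that resolve without care, and no definition of the event. The 2-to-6-day difference between arms rests on an assumed inpatient stay and measures exposure to the gap, not events lost. Bleeds that led to care should largely be caught by the existing items.

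The capsule part is smaller: Section 7.6 requires the question and Section 2.3.1 relies on the answer, but the follow-up form does not record it.

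**What to change.** In Section 18.12, for both arms:

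- Reword the black-stool, syncope, blood-in-stool and vomiting items to ask about the time since the patient left the ED or hospital at Day 7, and since the Day 7 call at Day 30.
- Record the date of onset for each positive answer.
- For CERA subjects, add one field: capsule passed, with yes, no or unsure as the answers.

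For a subject at home throughout, the windows would then cover 7/7 days at the first call and 23/23 at the second, 30/30 in total, against 2/30 now for the two 24-hour items. This is coverage of the calendar, not a forecast of additional re-bleeds found. Inpatient days continue to be covered by the in-person contact and chart review.

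The cost is a reworded form, one added field and slightly longer recall, with the imprecision that recall over up to 23 days brings. No clinical rule, visit or sample size changes.

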**Did you have an upper endoscopy after being discharged from the hospital? Yes No**

**What were the results of the endoscopy?**

Bleeding resolved

Bleeding persisted

New problem

Unsure

If patient has a new problem, please describe. \_\_\_\_\_

Did you have a return visit to the hospital? Yes No

Return date to the hospital? \_\_\_\_\_

Which Hospital? \_\_\_\_\_

Where you hospitalized for recurrent bleeding? \_\_\_\_\_

Did you have a second endoscopy? Yes No

What were the results? \_\_\_\_\_

When were you discharged? \_\_\_\_\_

### 18.13 Patient Chart Review

## Patient Chart Review

Initials of person abstracting information from chart \_\_\_\_\_

Hospital discharge date \_\_\_\_\_

Blood transfusion? Yes No

Date of transfusion \_\_\_\_\_

Number of PRBC? \_\_\_\_\_

Additional endoscopy Yes No

How many? \_\_\_\_\_

Hemostatic therapy? Yes No

Surgery? Yes No

Date of surgery \_\_\_\_\_

Please describe surgery. \_\_\_\_\_

Disposition?

Home  
Rehabilitation  
Nursing home  
Deceased

### 18.14 Adverse Event Form

## Adverse Event Form

Initials of person completing form \_\_\_\_\_

Start Date/Time \_\_\_\_\_

Stop Date/Time \_\_\_\_\_

During PillCam Administration Yes No

Post PillCam Administration Yes No

Please describe the AE \_\_\_\_\_

#### **Relationship to the Study Protocol/Procedures (Per Site PI)**

Unrelated

Unlikely

Possibly

Probably

Definite

---

#### **Relationship to the PillCam (Per Site PI)**

Unrelated

Unlikely

Possibly

Probably

Definite

---

#### **Primary Outcome**

Recovered/Resolved

Under Treatment

Change in AE/SAE Characteristic

Sequelae

Fatal

Unknown

---

Serious Event? Yes No

Life Threatening? Yes No

Required or prolonged hospitalization? Yes No

Disability? Yes No

Congenital Anomaly? Yes No

Required intervention? Yes No

Death? Yes No

Was Site PI notified? Yes No

Was the IRB notified? Yes No: If No, Why Not? \_\_\_\_\_

### 18.15 Protocol Deviation

## Protocol Deviation

Date of Event \_\_\_\_\_

Description of the Deviation \_\_\_\_\_

Reason for the deviation \_\_\_\_\_

Corrective measures \_\_\_\_\_

Was site PI notified? Yes No

Was IRB notified? Yes No

Why Not? \_\_\_\_\_
